## SYNOPSIS

Title	Wearable eye-tracking device as means of communication in the critically ill, and mechanically ventilated patient
Short Title	Eye-Control Trial
Principal Investigator	[name], PhD Assistant Professor, Department of Neurology and Neurosurgery, Division of Neurocritical Care Emory University School of Medicine
Study Description	The study will have two steps: (1) safety and efficacy phase, in which we will enroll up to 60 patients, with main goal to experience the use of the device in critical care settings, and better prepare for the second part (burn-in period); (2) a randomized controlled trial that will treat eligible and consented patients with either EyeControl or the current standard of care from a communication stand point. On a daily basis, all patients admitted will be screened according to the predefined inclusion/exclusion criteria. Eligible patients (or their LARs) will be approached by the study team to obtain consent. Once enrolled, and randomized to the intervention arm, the patients will be instructed how to use the EyeControl device and will keep the device on for as long as they would like. While on, the device will collect data as a potential monitor, such as time of wakefulness, and will screen for delirium by CAM-ICU questionnaire. At six months, we will contact the patient to assess his functional and cognitive performance using standardized questioners. Following this interview, the patient will end the participation in the trial.
Purpose	To determine the safety, tolerability, and ease of use of the EyeControl device and determine impact on communication and delirium in critically ill, ventilated patients in the intensive care unit.
Design	This is a single-center, Phase 1/2, two-step prospective, open-label, blinded-endpoint (PROBE) study evaluating the tolerability and efficacy of the EyeControl device.
Objectives	To evaluate the efficacy of a wearable communication device in preventing and treating ICU-delirium in critically ill patients who are admitted to the intensive care unit (ICU) and mechanically ventilated. The study will assess the safety, tolerability, and ease of use of the EyeControl device; examine its potential monitoring capabilities; determine the change in level of frustration and discomfort following use of the device; and measure long-term outcome of these critically ill patients.

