Outcome Measures	
For the burn-in phase, the primary outcome will be time to successful operation of the device (see below for definition), and secondary outcomes include length, type and intensity of use (e.g. use for communication, entertainment, call for help etc), safety, and proof of concept of non-communication features of the device such as wakefulness time monitoring and CAM-ICU capturing.
 
The primary end point of the second step will be number of alive and delirium days while in the ICU and on the ventilator up to 14 days from randomization, or to extubation or ICU discharge, the earliest. Secondary endpoints will include: proportion of patients who were able to operate and use EyeControl, the specific parameters of successful patients compared to those who were unable to operate it; the length and intensity of use; the correlation between the monitoring data and clinical data; and the cognitive and functional long term outcomes as assessed by telephone by the Critical care, Brain Dysfunction and Survivorship (CIBS Center from Vanderbilt University).

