#### EYE-CONTROL DEVICE

Currently, the solutions for communication deficits in mechanically ventilated patients are mainly using yes/no communication, attempting to write, and communication boards that allow people to point at defined pictures or letters (Khalaila et al., 2011). Recently, technological advancements led to incorporation of more sophisticated communication devices, proving the feasibility of an eye-tracking approach, for example (Carruthers et al., 2017).

The EyeControl is a new, wearable, eye-tracking device (Figure 2) that facilitates communication by means of internal feedback to the patients with a bone-conducting speaker. In this way, the device can ask the patient what he or she wants to say, and the patient replies by eye gestures such as blinking or moving the eyes in a certain direction. This approach eliminates the need for calibration, as most eye-tracking devices that use a screen require, and is relatively easy to operate. It is currently being tested in general ICU-based settings in Tel Aviv, Israel, where the company reports nearly 100% success in teaching patients to use the device within minutes.

**Figure 2:** The EyeControl device.

This device has other potential advantages that could be utilized in the critical care settings. It could be used as a monitor; for example, it could record times that the patient has her or his eyes open as a marker for wakefulness (it could be an important indirect marker for quality and length of sleep); it could use its communication with the patient to assess for delirium (using known basic questionnaires such as the CAM-ICU); it could assess, to some extent, the ability to follow commands with blinking and eye movements. The device could be part of the non-pharmacological interventions to prevent and treat delirium. For example, it could state the day, time, and location to the patients every few hours.

The risk associated with the device seems very low. It is external, wearable, and could be easily removed with any signs of discomfort. No significant side effect was recorded from using this device according to the manufacturer.

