### STEP 2:

**Primary goal:** Measure the time spent alive and non-delirious in the ICU up to 14 days from randomization with EyeControl-based communication compared with the standard of care, in a randomized-controlled fashion.

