As part of its operation, the device captures photographs and video of the patient's eyes (figure 3). In addressing the secondary goal of potential correlation between eye behavior and clinical events, we will explore this possibility by evaluating photographs of the eyes at the times of clinical events (i.e. hypoxia, new onset shock, or new onset sepsis). The device will activate the image data collection only after 50 consecutive frames of eye-in-the-image. This should be a safety index to verify that the device is only recording the eye. It will stop recording immediately when non-eye-in-the-image occurs. Data processing to decide if an eye is in the image is done locally on the device, so eventually only images of eyes should be collected. All external image data processing will be done following deidentification of the data, using the patient code only as an identifier.

Figure 3. Example photographs captured by the EyeControl device.

No randomization or blinding is planned for this step of the study, and no samples are planned to be collected.

---

**STEP 2: MEASURE REDUCTION IN DELIRIUM-FREE AND ALIVE DAYS IN THE ICU WITH EYECONTROL-BASED COMMUNICATION COMPARED WITH THE STANDARD OF CARE.**

The second step will be similar to the operation of the first one, in terms of patient screening and enrolling. The main difference will be the randomization process. Patients will be randomized to use EyeControl for as much as they wish, versus the standard of care. Randomization will be done centrally, and will be stratified to the specific unit, gender and age, race and ethnicity.

The primary goal of the second step will be to measure the time spent alive and non-delirious in the ICU with EyeControl-based communication compared with the standard of care. Delirium will be defined as CAM-ICU positive, starting at day 1 of use (following the day of training), up to 14 days from randomization or ICU discharge, the earliest. However, patients could require moderate to deep sedation following randomization, for example due to new or evolving medical complication. Whenever the RASS is below (-1), CAM-ICU will not be measured, and will be charted as undetermined. Therefore, only days in which the patient will be CAM-ICU positive, will be counted towards the primary outcome. CAM-ICU positive days prior to randomization will not be counted towards the primary outcome.

[figure not shown]
The secondary outcomes will include the following:

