### INCLUSION CRITERIA

- Intensive Care Unit (ICU) Admission
- Mechanically ventilated for at least 24 hours
- RASS between -1 to 1 at the time of screening (Note: minimal sedation is allowed including low-dose Fentanyl, Dexmedetomidine, Ketamine, Propofol, etc., as long as the RASS is in the predefined range).

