### Step 2:

Primary Outcome: The time spent alive and non-delirious in the ICU

Covariates/Confounders: age, gender, race, baseline education level, unit to which the patient was admitted to, need for tracheostomy, severity of illness by SOFA or APACHE score on admission and randomization day, categorical reason for admission (e.g. sepsis, ARDS, elective surgery, stroke etc), diagnosis of delirium prior to randomization and the presence of an acute central neurological injury.

Unadjusted Analyses: The time spent alive and non-delirious in the ICU will be evaluated using the stratified variant of the Mann-Whitney U test. In this analysis, patients will be stratified by ICU setting. For other variables, the unadjusted comparison will depend on the type of variable. In general, continuous variables will be compared using a Mann-Whitney U test and categorical variables will be compared using the  $\chi^2$  test.

Adjusted Analyses: The time spent alive and non-delirious in the ICU will be evaluated using a multi-level/mixed-effects quantile regression (median/50th percentile) while controlling for the previously listed covariates. The multi-level/mixed-effects model will be used to account for clustering within ICU setting. In the event that the regression fails to estimate properly, the covariates will be used to generate propensity scores and patients will be stratified into  $\geq 5$  propensity score strata. The time spent alive and non-delirious in the ICU will then be analyzed using the stratified variant of the Mann-Whitney U test. Analyses of the secondary outcomes will depend on the type of variable. Continuous variables will be analyzed using multi-level/mixed-effects quantile regressions (median/50th percentile), binary variable will be analyzed using multi-level/mixed-effects binary logistic regressions, ordinal scales will be analyzed using multi-level/mixed-effects ordinal (cumulative logit) logistic regressions.

Missing Data: In the event of substantial missing data, data will be imputed using a multiple imputation procedure. The type of procedure (e.g. fully conditional specification, hot decks etc.) and the number of imputed data sets will be determined by the amount of missing data and the pattern of missingness.

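### The Step 2 primary outcome starts counting the day after device training, an event only device-arm patients have; no common start is stated for both arms

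*Combined protocol and SAP*

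**What the plan says.** Under Study Design and Methods, Step 2, the protocol defines the outcome window: "Delirium will be defined as CAM-ICU positive, starting at day 1 of use (following the day of training), up to 14 days from randomization". Leaving the ICU sooner also closes the window. The same paragraph adds that "CAM-ICU positive days prior to randomization will not be counted towards the primary outcome".

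The Synopsis (Study Description) says who is trained: "Once enrolled, and randomized to the intervention arm, the patients will be instructed how to use the EyeControl device". The comparator is standard of care, with no device and so no training day.

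The other statements of the outcome give no start:

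- Study Purpose, Step 2: "Measure the time spent alive and non-delirious in the ICU up to 14 days from randomization".
- Synopsis, Outcome Measures: "up to 14 days from randomization, or to extubation or ICU discharge, the earliest".
- Statistical Analysis Plan, Step 2: "Primary Outcome: The time spent alive and non-delirious in the ICU", with neither a start nor an end.

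The Schedule of Events has CAM-ICU every 12 hours, from the Day 0 screening and enrolment column through the ICU admission.

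**The concern.** The window opens on a device event and closes on a randomization clock. Controls never have the opening event. Device patients who are never successfully trained may not have it either, and the plan expects some: comparing patients who could operate the device with those who could not is a Step 2 secondary endpoint in the Synopsis.

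The analyst must therefore supply a start that the plan does not state. If controls are counted from randomization and device patients from the day after training, the device arm has fewer countable days for reasons unrelated to delirium. Dropping never-trained patients would condition the primary comparison on a post-randomization event in one arm. Because the trial is open-label, this choice should not be left until data are in hand.

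The direction of the bias depends on what is scored. If alive, non-delirious days are counted (Study Purpose and SAP), a late start works against the device. If only CAM-ICU positive days are counted (the Step 2 design paragraph), it works in the device's favour.

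**Working it through.** **1. What each reading implies for the start**

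| Reading | Device arm | Controls | Gap |
|---|---|---|---|
| Literal | day after training | undefined | cannot be computed |
| Controls from randomization, training the same day | next day | randomization day | 1 day |
| Controls from randomization, training later | day after training | randomization day | more than 1 day |
| Training always on Day 0, controls also from Day 1 | Day 1 | Day 1 | none |

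The sentence excluding CAM-ICU positive days before randomization names no arm. It sets a floor, not a start. None of the last three rows is stated.

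**2. Inputs for an illustration**

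From Sample Size: mean 6.8 and SD 5.2 delirium/coma-free days over 14 days, a 2-day target, 80% power, alpha 0.05, 124 per arm.

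Assumed: two-sided test; minimal Mann-Whitney efficiency of 0.864 (the plan invokes the minimum but does not print it); constant daily accrual; unchanged SD; the same closing day in both arms; the whole device arm delayed by the same gap.

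**3. The plan's own figure**

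n per arm = 2 × [5.2 × (1.960 + 0.842) / 2]² = 106.1, rounded up to 107. Then 107 / 0.864 = 123.8, so 124 per arm and 248 in total. This matches the plan. (Without the intermediate rounding, 106.1 / 0.864 = 122.8, giving 246.)

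SE = 5.2 × √(2/124) = 0.660. For a 2-day effect, z = (2 / 0.660) × √0.864 = 2.815, and power = Φ(2.815 − 1.960) = 0.804.

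**4. A one-day gap, alive non-delirious days**

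- Daily accrual: 6.8 / 14 = 0.486.
- Shift against the device: 0.486 day, or 0.486 / 2 = 24% of the target.
- z for the shift: (0.486 / 0.660) × √0.864 = 0.684.
- No true effect, device appears worse: P(Z > 1.960 − 0.684) = P(Z > 1.276) = 0.101.
- No true effect, device appears better: P(Z < −1.960 − 0.684) = P(Z < −2.644) = 0.004.
- Two-sided rejection: 0.105.
- Power for a true 2-day benefit: the apparent effect is 2 − 0.486 = 1.514 days, giving 0.568.

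With the 244 patients given in the Synopsis (122 per arm), rejection is 0.104 and power 0.561.

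**5. Range**

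| Assumed gap | Shift (days) | Two-sided rejection, no effect | Power for 2 days |
|---|---|---|---|
| 0 | 0 | 5% | 80% |
| 1 day | 0.49 | 10.5% | 57% |
| 2 days | 0.97 | 28% | 30% |

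For a one-day gap, varying the assumed accrual from 0.3 to 0.8 day per day and the SD from 4.2 to 6.2 gives two-sided rejection from 6.4% to 28.6%.

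The documents give no daily rate for CAM-ICU positive days alone, so that scale is not computed.

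**The case against.** **Symmetric readings are open.** The randomization-based window in the Synopsis and Study Purpose does not distinguish arms. The Schedule of Events labels enrolment Day 0, so with same-day training the first day of use could be study Day 1 in both arms. This stands in part: the documents show an ambiguity, and a reader who infers that the plan mandates different windows goes beyond the text. But neither symmetric reading is written down for controls, and a start at randomization for everyone contradicts the one explicit start given.

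**Lags may be short.** Patients must have "RASS between -1 to 1 at the time of screening" and follow commands, and the company reports "nearly 100% success in teaching patients to use the device within minutes". This makes long delays less likely. It is, however, a company report from another site, and the plan itself measures time to first activation in Step 2. Even same-day training leaves a one-day gap if controls are counted from the randomization day.

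**The 10.5% is not a false-efficacy rate.** A reader might infer that the device is more likely to be declared beneficial by chance. On the scale computed, the opposite is true: false benefit falls from 2.5% to about 0.4%. Bias favouring the device arises only if CAM-ICU positive days are counted, and that cannot be sized here.

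**Fractional gaps do not fit.** It is tempting to model same-day training as a half-day gap. The rule counts days, so the randomization day counts or it does not.

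**Some material is unseen.** A figure beside the definition and the Step 2 flow schema are not readable here and might show timing by arm. The finding covers the text only.

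**Conclusion.** The point holds as a defect in the definition of the primary outcome. The only stated start is tied to a post-randomization event in one arm, and controls and never-trained device patients have none. This is more than missing detail, because the rule followed as written gives the two arms different footing.

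The size is conditional. The one-day result (shift 0.49 day, power about 57%, rejection about 10.5%, of which about 10.1 points are false apparent harm) requires that controls be counted from randomization, that every device patient open one day later, and that alive, non-delirious days be scored. It also borrows an accrual rate from a cohort followed for 14 days from admission, which may not suit awake patients enrolled later. With a common start the gap is zero and the planned power is intact. The documents do not establish which case would occur.

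**What to change.** In the Step 2 design paragraph, replace the start based on training and use with one start for all randomized patients in both arms. For example: *counted from the calendar day after randomization, regardless of whether or when the device is trained or used*. The randomization day would serve equally well if applied to both arms. Reword the exclusion sentence so that days before this common start are not counted.

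Add the same window to the SAP, which now has none, and to the Synopsis outcome measures and the Step 2 primary goal. Report training and first-use days only as device-use data.

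The cost is a few sentences. CAM-ICU is already scheduled every 12 hours from Day 0, so no new data are needed, and the sample size of 248 is unchanged. The downside is that device-arm days before training enter the comparison and may slightly dilute the effect.

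Two related inconsistencies need separate reconciliation: whether the window also closes at extubation (Synopsis) or only at ICU discharge (Step 2 design), and whether delirious or non-delirious days are scored. A common start does not settle either.

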## SAMPLE SIZE

From our retrospective analysis (described in the introduction), we expect about 130 patients per month for the initial screening (ventilated for at least two days). The same patient could be ineligible on a certain day, but become eligible later in the admission (e.g., due to the severity of the illness, the patient is deeply sedated for the first few days, and later sedation is weaned). This will allow us to recruit more patients, at different time points of their admission. Even with this in mind, it would be reasonable to assume that about half of these initially screened patients will not be eligible at any point of their admission due to any one of the exclusion criteria. Of those who will be eligible, we expect a high rate of consent, due to the low risk and the potential benefit of using the device while in the ICU. We therefore expect a rate of about 30 patients a month to be enrolled.

For the first step, we will plan to enroll up to 60 patients, and at least a third of the sample will be from the neuroscience ICU, and specifically patients with an acute brain injury

Given that there are no prior data, there is no clear criteria that would justify a specific number. We believe that having 40 to 60 patients work with this new device would be sufficient to draw initial conclusions about its use and specific indications according to the study aims as stated above.

For the second part of the trial, power calculations are based on previously published BRAIN-ICU trial. In that observational trial patients had  $6.8 \pm 5.2$  delirium/coma-free days within the first 14 days of admission, with an overall rate of about 50% rate of delirium. For the present trial, we considered a 2 day reduction in the time spent delirious as clinically significant. Given these parameters, the present trial will require 248 patients ( $N = 124$  per arm) to achieve sufficient power (80%,  $\alpha = .05$ ) to detect a 2 day difference. In general, a sample size of 248 will provide sufficient power to detect a standardized mean difference of 0.38 (assuming minimal asymptotic relative efficiency of Mann-Whitney U test), an odds ratio of 2.14 for binary variables (assuming maximal variance for a binomial distribution), and a Cohen's  $f$  of 0.18.

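### The Step 2 primary outcome never counts a day too deeply sedated for CAM-ICU as adverse, so an arm with more deep sedation would appear to have less delirium

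*Combined protocol and SAP*

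**What the plan says.** The scoring rule is in the Step 2 part of Study Design and Methods. The protocol foresees that "patients could require moderate to deep sedation following randomization, for example due to new or evolving medical complication". It then says: "Whenever the RASS is below (-1), CAM-ICU will not be measured, and will be charted as undetermined". The next sentence draws the consequence: "Therefore, only days in which the patient will be CAM-ICU positive, will be counted towards the primary outcome". The window there runs "up to 14 days from randomization or ICU discharge, the earliest".

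The outcome is labelled in two directions. The Synopsis gives the "number of alive and delirium days while in the ICU and on the ventilator up to 14 days from randomization", ending at extubation or ICU discharge if earlier. The Step 2 primary goal, the Step 2 design text and the Statistical Analysis Plan use time alive and not delirious; the SAP line reads "Primary Outcome: The time spent alive and non-delirious in the ICU".

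The Schedule of Events sets CAM-ICU every 12 hours. The Sample Size section takes its mean and SD from an observational study's "delirium/coma-free days within the first 14 days of admission", and sets the target thus: "we considered a 2 day reduction in the time spent delirious as clinically significant".

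**The concern.** Brain dysfunction too deep to be tested is a worse state than a clear-headed day, yet under this rule neither is adverse. Taken literally, a patient who falls below RASS -1 soon after randomization and stays there collects no delirium days, the best possible value.

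This matters because depth of sedation arises after randomization in an open-label trial. The intervention could change it: the Step 2 secondary goals plan to track treatment decisions prompted by the device's wakefulness data, which exist in one arm only. If the share of testable days differs between arms, the primary comparison mixes delirium with the opportunity to detect it. Blinded assessment would not help, because RASS decides whether CAM-ICU is done at all.

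**Working it through.** **1. The plan's own sample size.** Inputs from Sample Size: difference 2 days, SD 5.2, power 80%, alpha 0.05 (two-sided reproduces the figure), and the minimal Mann-Whitney efficiency, which is 0.864.

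- Normal approximation: 2 × (5.2 × (1.960 + 0.842) / 2)² = 106.1 per arm; 107 with the t correction.
- 107 / 0.864 = 123.8, so 124 per arm and 248 in total. This agrees with the plan.
- Detectable standardized difference at 124 per arm: 0.383, against the stated 0.38.

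The number is right for its inputs. But the SD of 5.2 belongs to delirium/coma-free days, whose name excludes coma days from the favourable count. The Step 2 rule makes no such exclusion.

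**2. How a wholly undetermined day scores (patient alive, RASS below -1 at both assessments).**

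- Count of delirium days: adds 0.
- Alive, non-delirious time, taken as observed time minus positive days: adds 1 favourable day.
- Alive, non-delirious time, taken to require a negative CAM-ICU: adds 0 favourable days. Only this reading removes the false advantage, and it is not written anywhere.

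The SAP does not settle the matter. It does not mention undetermined assessments, its covariates include no sedation or coma after randomization, and its imputation clause applies only to substantial missing data, with the method left open.

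**3. Size under the first two readings, with no true device effect.** Let D be observed days per patient, p the delirium risk on a testable day, and x the extra share of wholly undetermined days in one arm. Then:

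spurious shift = D × p × x

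All three inputs are assumptions. The 50% in Sample Size is an overall delirium rate, not a daily one, so p runs from 0.3 to 0.7. D = 14 is the ceiling. D = 7 represents a shorter stay: the Background gives a mean of 8.6 ventilator days for patients ventilated at least two days, part of which precedes randomization. With x = 0.20:

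| p | D = 14 | D = 7 |
|---|---|---|
| 0.3 | 14 × 0.3 × 0.2 = 0.84 days | 7 × 0.3 × 0.2 = 0.42 days |
| 0.5 | 1.40 days | 0.70 days |
| 0.7 | 1.96 days | 0.98 days |

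Against the 2-day target this is 42% to 98% over 14 days and 21% to 49% over 7.

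**4. What such a shift could do to the test (D = 14, x = 0.20).** Effective size is 124 × 0.864 = 107.1 per arm, and the standard error is 5.2 × √(2/107.1) = 0.71. The chance of a significant result favouring the more sedated arm is about 22%, 50% and 79% for p = 0.3, 0.5 and 0.7. At p = 0.5 with x = 0.10 it is about 17%. A Mann-Whitney simulation at p = 0.5 (124 per arm, 14 days, 10% versus 30% undetermined days, SD about 5.0) gave 61%.

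**5. The same data with undetermined days not favourable.** The more sedated arm now loses D × (1 − p) × x favourable days: 14 × 0.5 × 0.2 = 1.4 at p = 0.5. In the simulation it was never significantly favoured, and was significantly disfavoured in 62% of runs. The composite is therefore not neutral to sedation; it counts it openly as adverse.

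**The case against.** Several points on the other side stand.

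- A reader might infer that any RASS below -1 turns the day into a good one. The rule works per assessment and CAM-ICU is done every 12 hours, so a day with one positive and one undetermined result would presumably count as positive. Only days without a testable positive result are affected.
- A reader might infer that the flaw persists however the endpoint is reconciled. It does not: undetermined is charted as its own category, and a definition requiring a negative CAM-ICU would remove the false advantage. But no section states that definition, and the sentence counting only positive days points the other way.
- A reader might infer that the device arm will gain, or that a false positive is likely. No arm difference in sedation is documented. The protocol's example, a new complication, is not arm-specific, and patients must be at RASS -1 to 1 and following commands at screening. Prolonged deep sedation throughout is an extreme case. The probabilities in the working hold only under their assumed inputs.
- Keeping sedation apart from delirium is a disclosed choice that fits a delirium hypothesis, and a composite penalises sedation that was clinically needed. That is a reason to show components, not to leave the day unscored.
- The documents do not define coma, so it cannot be shown that RASS below -1 equals the coma component of the planning variable.

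The Step 1 text says sedative use will be taken into account in the final analysis. That is partial mitigation at most, since it sets no scoring rule.

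**Conclusion.** The concern holds in this form: under the written rule, a day with no testable positive CAM-ICU is never adverse, so deeper sedation in one arm would appear as less delirium in that arm. The exception would be a requirement of a negative CAM-ICU, which is not written. The scored variable also differs, on exactly this point, from the one used to size the trial, although the 248 itself reproduces.

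For an assumed 20-point difference in undetermined days and a daily delirium risk of 0.3 to 0.7, the spurious shift is 0.84 to 1.96 days over 14 observed days and 0.42 to 0.98 over 7. The direction between arms is unknown and the shift is zero if sedation is balanced. Because this is the primary endpoint and sedation can respond to the intervention, the scoring should be settled before Step 2 randomization begins.

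**What to change.** First reconcile the endpoint's direction and stop date across the Synopsis, the Step 2 design text and the SAP. Then define each day of the 14-day window:

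- **Favourable:** alive, at least one assessable CAM-ICU, and none positive.
- **Not favourable:** any positive CAM-ICU; wholly undetermined because RASS was below -1; or dead. These are observed states and are not imputed. An assessment missed although RASS allowed it is missing data and goes to the missing-data rule.
- **After extubation or ICU discharge:** one stated rule for all patients within the window. If favourable days were counted only up to that point, early recovery would be penalised. The Schedule of Events places CAM-ICU at screening and in the ICU stay, so days after ICU discharge need a convention.

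Report undetermined, delirious and dead days by arm as components, and keep the CAM-ICU-positive-day count as a sensitivity analysis. State that the 5.2-day SD is carried over from a similar but not identical variable.

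Cost: mainly protocol and SAP wording, since CAM-ICU is scheduled and RASS is in nursing charting; the post-discharge rule does require a decision. The downside is that clinically needed sedation counts as unfavourable, which is why the components must accompany the result. The match to the planning variable remains approximate.
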